
TREATMENT DURATION
	
Participants are planned to be treated with Debio 1143 and nivolumab for up to 52 weeks (13 cycles), until any of the following events occurs: symptomatic PD, asymptomatic but confirmed PD (as per iRECIST), unacceptable toxicity per Investigator judgment and despite up to two dose adjustments, patient withdrawal, or treatment delay greater than 4 and 8 weeks (+1 week tolerance) for Debio 1143 and nivolumab, respectively.
 
Permission to prolong the study treatment for one additional year can be exceptionally granted by the Sponsor, if patients are deriving continuous clinical benefit from the study treatment. Medical justification for extending the treatment and the assessment of the risk/benefit balance must be provided by the Study Investigator and will be discussed with the Sponsor. The decision to further extend study treatment will be re-evaluated on a yearly basis for each patient.
 
Re-treatment criteria are listed in Table 2.
 
From Cycle 2, if a patient does not meet the requirements for treatment continuation on Day 1 of any cycle, both study drugs will be withheld until recovery or for a maximum of 4 and 8 weeks (+1 week tolerance window) for Debio 1143 and nivolumab, respectively. After this delay-period, the patient should withdraw from treatment.
 
If a patient does not meet the requirements for treatment continuation on any days other than D1 (D2-10 or D15-24), treatment will be immediately interrupted and the corresponding Debio 1143 dose (and nivolumab if on D15) will be omitted. Patients should be re-assessed (ideally every 48-72 hours, if clinically indicated) and treatment will only be resumed after all re-treatment criteria are met.
 
All patients who withdraw from treatment for any reason will be followed for safety up to 5 months (<math>\pm 15</math> days) after the last nivolumab infusion, complete resolution or stabilization of any ongoing toxicity, unless the patient starts a new treatment, end-of-life-care or withdraws consent.
 
If for any reason, treatment with nivolumab is temporarily withheld, Debio 1143 may be continued; however, at any time, and regardless of the reason, if nivolumab is permanently discontinued then Debio 1143 must also be withdrawn. If for any reason Debio 1143 is withheld temporarily, nivolumab will also be withheld until treatment may be resumed. Patients will not receive any further nivolumab infusions during the study until Debio 1143 treatment is resumed.

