If a patient does not meet the requirements for treatment continuation on any day other than D1 (D2-10 or D15-24) of any cycle, treatment will be immediately interrupted and the corresponding Debio 1143 dose (and nivolumab if on D15) will be omitted. Patients should be re-assessed, ideally, every 48-72 hours, if clinically indicated, and treatment will only be resumed after all re-treatment criteria are met. On D1, treatment can be delayed more than 3 days if required; in this case, the assessment schedule will shift accordingly, and all assessments planned for D1 will be performed on the day treatment is re-started. However, if treatment is interrupted during any day other than D1 and the re-treatment criteria are not met within 72 hours, treatment will be resumed only on D1 of the next cycle.

A maximum delay of 4 and 8 weeks (+1-week tolerance) for Debio 1143 and nivolumab, respectively, is allowed. After this delay-period, treatment will be withdrawn. Patients withdrawing from treatment for any reason will be followed for safety up to 5 months (±15 days) after the last nivolumab infusion, complete resolution or stabilization of any ongoing toxicity, unless the patient starts a new treatment, end-of-life-care or withdraws consent.

Patients experiencing immune-related AEs, that require withholding nivolumab infusions temporarily until resolution to at least Grade 1, may withhold nivolumab for a maximal period of up to 8 weeks (±1 week

tolerance). During this period, patients may continue to receive Debio 1143 as per protocol, if appropriate. Patients requiring more than 8 weeks ( $\pm 1$  week) of nivolumab interruption and those who permanently discontinue nivolumab for any reason, will discontinue Debio 1143 permanently and will be withdrawn from the study. The nivolumab dose will not be adjusted under any circumstances.

Patients experiencing any treatment-related grade 4 toxicity (clinically or laboratory, excluding grade 4 amylases and/or lipase and/or non-febrile neutropenia) will withdraw from treatment definitively without further reduction (see [section 8.3.2.1](#) for details).

Patients experiencing any other treatment-related toxicity fulfilling applicable DLT criteria (as shown below) at any time during the study must stop treatment and may only resume treatment after adequate recovery to re-treatment criteria.

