Treatment must be re-started with a Debio 1143 dose reduction. Individual patients may have up to two dose adjustments of 50 mg/d (each one) up to a minimum dose of 100 mg/d Debio 1143 (i.e. 1st dose reduction 150 mg/d, 2nd dose reduction 100 mg/day). Patients still requiring a dose adjustment with a dose of 100 mg/d will be withdrawn from the study. Once adjusted, Debio 1143 dose will not be re-escalated under any circumstances.

Up to 2 dose reductions must be implemented in the event of any of the following:

- Any Debio 1143-related Grade 4 hematologic toxicity
- Debio 1143-related febrile neutropenia any grade, or Grade 3 thrombocytopenia if associated with bleeding or requiring platelet transfusion
- Debio 1143-related grade 2 or higher alanine transaminase (ALT)/ aspartate transaminase (AST) increase with a concurrent increase of total bilirubin  $\geq 2$  x upper limit of normal (ULN) and concurrent with alkaline phosphatase (ALP)  $\leq 2$  x ULN (Hy's law), in the absence of objective causes of biliary obstruction due to obvious disease-related causes
- Any Grade 3, treatment-related, non-hematologic clinical toxicity lasting 3 or more days despite optimal supportive care, or requiring admission for appropriate medical management; hypersensitivity and/or infusion-related reactions are excluded if not reoccurring after appropriate pre-medication and/or prolonging infusion time
- Grade 3 non-hematologic laboratory value (excluding lipase, amylase and/or autoimmune endocrinopathies manageable by replacement therapies)
- A delay of  $>2$  weeks due to drug-related toxicity in initiating subsequent cycles, or a second delay lasting  $>24$  h but  $<2$  weeks
- Unable to complete at least 70% of the scheduled treatment, i.e. more than six Debio 1143 skipped doses during any cycle due to treatment-related toxicity or more than 2 treatment interruptions  $>24$  h but  $<6$  days

If for any reason Debio 1143 is withheld temporarily, nivolumab will also be withheld until treatment may be resumed. Patients discontinuing Debio 1143 definitively for any reason will also discontinue nivolumab study treatment.

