#### 8.3.2.1. End of treatment

Treatment with Debio 1143 will be continued until any of the following occurs:

1. Unacceptable toxicity [including, treatment-related NCI-CTCAE v5.0 grade 4 laboratory abnormalities (excluding hematological and/or non-febrile asymptomatic neutropenia/leukopenia)] that does not resolve with appropriate standard medical measures; or intercurrent illness that would, in the opinion of the Investigator, affect assessments of clinical status to a significant degree or compromise the patient's safety;
2. Permanent discontinuation of nivolumab;
3. Treatment delay greater than 4 and 8 weeks (+1-week tolerance) for Debio 1143 and nivolumab, respectively;
4. Need to discontinue Debio 1143 due to toxicity despite dose reduction to 100 mg/d;
5. Prohibited medication as indicated in [section 7.7.2](#) is required/used during the course of the trial. In the event a patient is found to be taking a prohibited medication during the trial, the site should immediately contact the medical monitor. The decision to withdraw the patient will be made in conjunction with the Sponsor;
6. If a critical protocol violation occurs that may preclude safety continuation of the study for the patient, the Sponsor's trial manager will be contacted to discuss if the patient has to be withdrawn from treatment;
7. Symptomatic disease progression documented by RECIST v1.1 or by GCIG criteria (Cohort 4, if applicable) in RECIST non-evaluable patients. However, patients may continue study treatment if, in the Investigator's opinion, there is reasonable evidence of ongoing clinical benefit or suggestion of "pseudoprogression" without excess risk of toxicity or complications for the patients.
8. Confirmed disease progression as per iRECIST;
9. Any medical condition that the Investigator or Sponsor determines may jeopardize the patient's safety if he or she continues in the study;
10. Withdrawal of patient's consent;
11. Pregnancy or breast-feeding a baby;
12. Start of any subsequent anti-neoplastic therapy (excluding palliative symptomatic localized RT up to 36 Gy total doses for alleviating symptoms e.g. pain, intracranial hypertension, which may continue upon the Sponsor's agreement, if appropriate). These patients will continue only in the OS follow-up.

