### 8.3.2.2. Follow-up

Patients with confirmed PD at the EOT visit will have an safety follow-up of 5 months ( $\pm 15$  days) planned after the last nivolumab infusion, provided no new cancer treatment or end-of-life care has been started, otherwise this visit may be done immediately before if any of these occur. Patients without PD documented at the EOT visit will continue in follow-up for efficacy every 12 weeks ( $\pm 1$ -week window) until PD or start of new treatment or end-of-life care, whichever occurs first. After PD or new cancer treatment or end-of-life care starts, patients will not attend more onsite visits, however, they and/or relatives may be contacted (by telephone, email or mail) every 4 ( $\pm 1$ ) months to update the survival status until the end of the Main study period (18 months have elapsed since the LPI was included in the study or 60 days after LPLV, whichever occurs first).

- Follow-up assessments comprise onsite visits:
- Safety: For all patients, one first safety follow-up visit will be conducted 90 days ( $\pm 15$  days) after last study treatment; a second safety follow-up visit will be scheduled at 5 months ( $\pm 15$  days) after the last nivolumab infusion, provided the first safety follow-up visit did not overlap ( $\pm 1$  week), and if the patient is still alive and no further anticancer treatment has been started yet..
- Efficacy: Patients without evidence of PD at EOT will be assessed for PD by appropriate methods (CT scan or MRI, and clinically) every 12 weeks ( $\pm 1$  week) until symptomatic PD or confirmed iRECIST PD or start of any new cancer treatment or end-of-life care or the end of the Main study period, whichever occurs first. For patients who continue study treatment after the Main study period, tumor response assessments will continue at the frequency of local institutional care practice until PD, start of any new anti-cancer therapy, death or EOT, whichever occurs first.
- Survival calls/contact: All patients alive after symptomatic progression or confirmed iRECIST PD or start of new anti-cancer treatment will be contacted (by telephone, e-mail or mail) every 4 ( $\pm 1$ ) months until the end of the Main study period. In case patients cannot be reached, the primary physician or the patient's partner or family may be contacted by the Investigator or designee.

The following scheme summarizes the temporal relationship between EOT and EOS:

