#### **8.4. Study duration and EOS**

The study duration for an individual patient completing 13 cycles, will be 52 weeks plus up to 5 months for safety follow-up after EOT, excluding a 4-week screening period. Patients will attend the EOT as well as any follow-up visits, if applicable.

Permission to prolong the study treatment for one additional year can be exceptionally granted by the Sponsor, if patients are deriving continuous clinical benefit from the study treatment. Medical justification for extending the treatment and the assessment of the risk/benefit balance must be provided by the Study Investigator and will be discussed with the Sponsor. The decision to further extend study treatment will be re-evaluated on a yearly basis for each patient.

The total number of onsite visits per patient will depend on the total number of cycles delivered which is based on disease progression, clinical deterioration, investigator criteria, unacceptable toxicity or death whichever occurs first.

The EOS will occur at the End of Main study period or End of Extended study period, whichever occurs last.

The Sponsor will make every effort to supply Debio 1143 and nivolumab to patients who benefit from continued treatment; Safety of the patients will be monitored and Health authorities will be notified per regulatory requirements.

Patients will discontinue the study for any of the following reasons:

1. Patient withdrawal of consent;
2. Patient lost to follow-up;
3. Start of end-of-life care;
4. Death;
5. Sponsor or Institutional Review Board (IRB)/ Independent Ethics Committee(s) (IEC) decides to terminate early the study;
6. Completion of Main study period, or completion of Extended study period, as applicable.

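### Section 5.4 withdraws patients from the study for events that the rest of the protocol treats as end of treatment with follow-up continuing

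*Protocol*

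**What the plan says.** Protocol section 5.4 (Dose modifications) contains two sentences that end study participation. The first covers patients who need more than 8 weeks of nivolumab interruption and "those who permanently discontinue nivolumab for any reason, will discontinue Debio 1143 permanently and will be withdrawn from the study". The second reads "Patients still requiring a dose adjustment with a dose of 100 mg/d will be withdrawn from the study".

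Other text describes the same events differently:

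- **Section 5.4, the paragraph before the first sentence:** "Patients withdrawing from treatment for any reason will be followed for safety up to 5 months" after the last nivolumab infusion. The stated exceptions are new treatment, end-of-life care and withdrawal of consent.
- **Synopsis, treatment duration:** "if nivolumab is permanently discontinued then Debio 1143 must also be withdrawn", with no mention of leaving the study. The same row adds "All patients who withdraw from treatment for any reason will be followed for safety up to 5 months".
- **Section 8.3.2.1 (End of treatment):** item 2 of the reasons for ending Debio 1143 is "Permanent discontinuation of nivolumab". Item 3 is an over-long treatment delay, and item 4 is a need to stop Debio 1143 for toxicity after reduction to 100 mg/d. An end-of-treatment (EOT) visit follows for every listed reason.
- **Section 8.3.2.2 (Follow-up):** a 90-day safety visit for all patients, a conditional visit at 5 months, and survival contact every 4 months. For efficacy, "Patients without PD documented at the EOT visit will continue in follow-up for efficacy every 12 weeks".
- **Section 8.4:** "Patients will discontinue the study for any of the following reasons", followed by six items: consent withdrawn, lost to follow-up, end-of-life care, death, early termination of the study, and completion of the study period.

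**The concern.** Leaving treatment and leaving the study are different events, and the protocol otherwise keeps them apart. SAP section 10.1 also tabulates them separately, each with its own reasons. Section 5.4 is where an investigator looks when toxicity forces a decision, and its wording is directive. The layout elsewhere does not help: the end-of-treatment rules sit under a parent heading (8.3.2) named for study discontinuation.

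A site that follows 5.4 literally would close the patient out. Many of these patients will have stopped nivolumab for immune toxicity, since Table 7-2 orders permanent cessation of study treatment for most Grade 3-4 immune-related events and for cardiac events from Grade 2. Their scheduled follow-up would then end for a reason tied to their clinical course, and sites could differ in what they do.

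**Working it through.** The plan gives no figure on this point and no arithmetic applies. The check sets the passages side by side.

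**Step 1. Status assigned to each trigger**

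| Trigger | Section 5.4 | Section 8.3.2.1 | Listed in 8.4? |
|---|---|---|---|
| More than 8 weeks of nivolumab interruption | leaves the study | ends treatment (item 3) | no |
| Permanent nivolumab stop, any reason | leaves the study | ends treatment (item 2) | no |
| Further adjustment needed at 100 mg/d | leaves the study | ends treatment (item 4, the corresponding event) | no |

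Section 8.4 does not call its list exhaustive, but it has no catch-all item that would take in these events. Section 5.4 also disagrees with itself. Besides the 5-month safety rule, its next paragraph takes patients with treatment-related Grade 4 toxicity (with stated exceptions) off treatment only, although they too stop nivolumab for good.

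**Step 2. What survives a literal reading of 5.4**

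- Section 9.2.2 keeps serious adverse events (SAEs) reportable for 5 months after the last nivolumab infusion, under a heading about post-study reporting. A fatal outcome is an SAE criterion (9.1.2), so deaths from adverse events in that window remain reportable.
- Section 9.3 requires SAEs to be followed to resolution, stabilization or explanation. The clause that disregards study participation is attached to the last of these.
- Section 8.2.2.1 runs adverse event recording to 5 months after the last nivolumab dose, and the treatment-emergent window (protocol 11.4.1.2, SAP 18.1) is dated the same way. Neither is tied to study status.
- Section 8.3.2.1 requires patients taken off treatment for adverse events to be followed, with the outcome recorded.

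**Step 3. What a literal reading puts at risk**

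- *Scheduled safety visits and laboratory tests.* Without visits, non-serious events have no fixed occasion for collection. The nivolumab events of special interest (9.1.6) include suspected immune-related events that need not be serious.
- *Scans after the EOT visit.* SAP 17.2.1.5 censors PFS at the last adequate assessment when no progression or death is documented. A patient who stopped for toxicity without progression would be censored for a toxicity-related reason. A patient who stopped because of progression already has the PFS event, so PFS is unaffected.
- *Survival contact.* SAP 17.2.1.7 censors OS at the date last known alive. The OS sensitivity analyses in SAP 17.2.4 address only new anti-cancer therapy and COVID-19 death, so neither would test this censoring.

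Kaplan-Meier estimation assumes that censoring is unrelated to the later outcome. Censoring at a toxicity-driven withdrawal may breach that assumption, and the documents do not show in which direction the estimates would move.

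**The case against.** The strongest reply is that the word for the study in 5.4 is a slip for study treatment. Most of the protocol points that way. A literal reading would also apply to nearly everyone, because each treated patient eventually stops nivolumab, and section 8.3.2.2 would then have almost no one left to follow. This is a persuasive inference, but the documents do not state it. The wording appears twice in the operative section, so a probable intention elsewhere does not remove the conflict.

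Two stronger readings are tempting, and neither is supported.

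- *A reader might infer that patients with severe immune toxicity drop out of observation altogether.* They do not. The SAE and adverse event provisions in Step 2 continue on their own terms.
- *A reader might size the problem* by applying the 18.0% Grade 3/4 treatment-related rate in section 3 to 60 Part B patients (0.18 × 60 = 10.8). That rate comes from first-line NSCLC and measures toxicity, not permanent discontinuation. Table 7-2 only withholds nivolumab for a first Grade 3 diarrhea, colitis or skin event and for Grade 3-4 endocrinopathies. Sixty is also the maximum, reached only if no cohort is futile, and SAP section 4.3 refers to futility of the Part B cohorts.

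**Conclusion.** The concern holds as a contradiction in operative text. Section 5.4 assigns study withdrawal to three events that 8.3.2.1 and 8.3.2.2 treat as end of treatment with follow-up, that 8.4 does not list, and that fall under the 5-month safety rule in 5.4 itself and the synopsis.

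The consequence is moderate and conditional on a site applying 5.4 literally. It would then be loss of scheduled safety visits and laboratory tests, incomplete capture of non-serious adverse events and events of special interest, loss of scans after the EOT visit with early PFS censoring, and loss of later survival contact with early OS censoring. SAE reporting and follow-up would remain. The documents give no permanent-discontinuation rate, so no patient count can be attached.

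A reader might also infer damage to the primary endpoint, because SAP 17.2.1.3 requires confirmation of response at least 4 weeks later. That could touch only a patient whose response was still unconfirmed when withdrawn. The documents give no basis for sizing it, and the conclusion does not rest on it.

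**What to change.** Reconcile the two sentences in section 5.4 with sections 8.3.2.1, 8.3.2.2 and 8.4, so that the protocol gives these patients one study status and the follow-up already scheduled in 8.3.2.2 is not cut off. A cross-reference from 5.4 to 8.3.2.2 would make the status clear where investigators make the decision. Nothing here proposes a change to when either drug is interrupted, reduced or stopped.

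The cost is wording in a protocol amendment. No visits, scans or contacts are added, and no analysis changes. If patients have already been closed out under the 5.4 wording, the sponsor should identify them from the end-of-study records and state in the report how their PFS and OS were censored.

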
DLT PERIOD AND DEFINITION OF DLTS
	
The DLT period is defined as Cycle 1*.
 
DLT is defined as any of the following treatment-emergent adverse events (TEAEs) which are possibly, probably or definitely related to the combination treatment and occurring in Cycle 1 (1 cycle=4 weeks):
 
 
• Any Grade 4 or 5 hematologic toxicity, clinical or laboratory non-hematologic toxicity
 
• Febrile neutropenia any grade, Grade 3 thrombocytopenia if associated with bleeding or requiring platelet transfusion
 
• Grade 2 or higher cardiac or neurologic toxicities, pneumonitis that does not resolve within 3 days after starting steroids at adequate doses or that was recurrent upon steroid tapering or withdrawal, myasthenia gravis, myositis, polymyositis, Guillain-Barre syndrome (excluding peripheral purely-sensory neuropathies)
 
• Grade 2 or higher alanine transaminase (ALT)/ aspartate transaminase (AST) increase with a concurrent increase of total bilirubin <math>\geq 2</math> x upper limit of normal (ULN) and concurrent with alkaline phosphatase (ALP) <math>\leq 2</math> x ULN (Hy's law), in the absence of objective causes of biliary obstruction due to obvious disease-related causes
 
• Any other Grade 3 non-hematologic, treatment-related clinical toxicity lasting 3 or more days despite optimal supportive care, or requiring admission for appropriate medical management; hypersensitivity and/or infusion-related reactions are excluded if not reoccurring after appropriate pre-medication and/or prolonging infusion time
 
• Grade 3 non-hematologic laboratory value (excluding lipase, amylase and/or autoimmune endocrinopathies manageable by replacement therapies) if:             
 
a. Symptomatic and
 
b. Medical intervention was promptly required to treat the patient, or
 
c. The abnormality led to hospitalization or
 
d. The abnormality did not resolve to at least Grade 1 within 2 weeks (including the steroid tapering period) despite adequate medical intervention/treatment
 
 
 
• A delay of >2 weeks due to drug-related toxicity in initiating Cycle 2
 
• Unable to complete at least 70% of the scheduled treatment, i.e., more than six Debio 1143 skipped doses in Cycle 1 due to treatment-related toxicity
 
• Required dose reduction in Cycle 1 or on Cycle 2 Day 1 or requirement for treatment withdrawal due to treatment-related toxicity (even if not meeting other DLT criteria)
 
 
* Any toxicity fulfilling one or more of these criteria but occurring from C2D1, may be defined as delayed DLTs after discussion and agreement between Principal Investigators (PIs), DSMC and the Sponsor, and may be considered for RP2D definition, if appropriate.

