## 5.2. DLT period and definition of DLTs

The DLT period is defined as Cycle 1\*.

DLT is defined as any of the following treatment-emergent adverse events (TEAEs) which are possibly, probably or definitely related to the combination treatment and occurring in Cycle 1 (1 cycle=4 weeks):

- Any Grade 4 or 5 hematologic toxicity, clinical or laboratory non-hematologic toxicity
- Febrile neutropenia any grade, Grade 3 thrombocytopenia if associated with bleeding or requiring platelet transfusion
- Grade 2 or higher cardiac or neurologic toxicities, pneumonitis that does not resolve within 3 days after starting steroids at adequate doses or that was recurrent upon steroid tapering or withdrawal, myasthenia gravis, myositis, polymyositis, Guillain-Barre syndrome (excluding peripheral purely-sensory neuropathies)
- Grade 2 or higher alanine transaminase (ALT)/ aspartate transaminase (AST) increase with a concurrent increase of total bilirubin  $\geq 2$  x upper limit of normal (ULN) and concurrent with alkaline phosphatase (ALP)  $\leq 2$  x ULN (Hy's law), in the absence of objective causes of biliary obstruction due to obvious disease-related causes
- Any other Grade 3 non-hematologic, treatment-related clinical toxicity lasting 3 or more days despite optimal supportive care, or requiring admission for appropriate medical management; hypersensitivity and/or infusion-related reactions are excluded if not reoccurring after appropriate pre-medication and/or prolonging infusion time
- Grade 3 non-hematologic laboratory value (excluding lipase, amylase and/or autoimmune endocrinopathies manageable by replacement therapies) if:
  - a. Symptomatic and
  - b. Medical intervention was promptly required to treat the patient, or
  - c. The abnormality led to hospitalization or
  - d. The abnormality did not resolve to at least Grade 1 within 2 weeks (including the steroid tapering period) despite adequate medical intervention/treatment
- A delay of >2 weeks due to drug-related toxicity in initiating Cycle 2
- Unable to complete at least 70% of the scheduled treatment, i.e. more than six Debio 1143 skipped doses in Cycle 1 due to treatment-related toxicity
- Required dose reduction in Cycle 1 or on Cycle 2 Day 1 or requirement for treatment withdrawal due to treatment-related toxicity (even if not meeting other DLT criteria)

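### The conditions that limit when a Cycle 1 Grade 3 laboratory value is a DLT (Protocol 5.2) are nearly cancelled by the dose-reduction rules in Protocol 5.4

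*Protocol*

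**What the plan says.** **DLT definition (Protocol 5.2; repeated in the synopsis).** Any one listed item, if related, is enough. The laboratory bullet covers Grade 3 non-haematologic values other than lipase, amylase and replaceable endocrinopathies. It applies only under conditions: (a) symptomatic and (b) needing prompt intervention, or (c) hospitalisation, or (d) "The abnormality did not resolve to at least Grade 1 within 2 weeks". A separate bullet covers "more than six Debio 1143 skipped doses in Cycle 1 due to treatment-related toxicity". The last bullet begins "Required dose reduction in Cycle 1 or on Cycle 2 Day 1", adds required withdrawal, and applies "due to treatment-related toxicity (even if not meeting other DLT criteria".

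**Dose modifications (Protocol 5.4).** The list of events that require a reduction includes "Grade 3 non-hematologic laboratory value (excluding lipase, amylase and/or autoimmune endocrinopathies manageable by replacement therapies", with no conditions attached. The lead-in to the stop-and-restart rule refers to toxicity "fulfilling applicable DLT criteria (as shown below". Two later sentences pull apart. One lets a single interruption of up to 3 days resume at the same dose. The other requires adjustment after any interruption for a related Grade 3 toxicity, and its exceptions name no chemistry value. Table 5-3 allows Debio 1143-related events of at most Grade 2 on Days 2-10 and 16-24, and at most Grade 1 (with listed exceptions) on Days 1 and 15; otherwise dosing stops. If the criteria "are not met within 72 hours, treatment will be resumed only on D1 of the next cycle".

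**Cycle 2 delay.** The text after Table 5-3 counts any related delay in starting Cycle 2 as a DLT. Section 5.2 requires a delay of more than 2 weeks.

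**SAP 18.1.2.** A DLT is a TEAE ticked as such in the eCRF, to be confirmed at the escalation decision. No rule is given that settles the conflict.

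**The concern.** A related, asymptomatic Grade 3 chemistry value that settles quickly does not meet the laboratory bullet. It can still become a DLT in two steps: 5.4 requires a reduction, and 5.2 counts the required reduction. Conditions written into two places to narrow a criterion are then overridden by another section.

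This matters because the Part A primary endpoint, the RP2D, rests on a DLT proportion below one third (Protocol 8.1.1.1), alongside safety, PK and compliance (4.1.1). The event class is realistic. Protocol 2.3 reports that the one DLT in the extended daily-dosing experience was an asymptomatic, reversible transaminase elevation at 200 mg/d, the dose of level 2 here, although it gives no grade.

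**Working it through.** **1. The two routes for one event** (related, non-excluded, asymptomatic, resolving within 2 weeks, no admission)

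| Step | Laboratory bullet alone | Through 5.4 |
|---|---|---|
| Conditions (a and b), c or d | not met | not asked |
| Reduction required? | – | yes: laboratory bullet in 5.4, and the Grade 3 adjustment sentence after a Table 5-3 interruption |
| Last 5.2 bullet | – | met |
| DLT? | no | yes |

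Reading the conditions as a and (b, c or d) instead leaves the conflict in place.

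**2. Where the wording decides the outcome.** Dosing on Days 1-10 and 15-24 gives 20 doses; the skipped-dose DLT limit is more than 6. Scheduled Cycle 1 laboratory days after the first dose are 3, 8, 15, 17 and 22 (Protocol 8.2.2.5; Days 3 and 17 in Part A only). Doses lost if dosing stops that day and waits for Cycle 2:

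- Day 3: 8 + 10 = 18
- Day 8: 3 + 10 = 13
- Day 15: 10
- Day 17: 8
- Day 22: 3

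The first four exceed 6, so a stop that outlasts 72 hours is a DLT anyway through the skipped-dose bullet. If dosing resumes at 72 hours, at most 3 doses are lost. The conflict therefore decides mainly values that settle within about 3 days.

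Day 22 is the exception. Cycle 2 Day 1 is Day 29, 7 days later. A value back to Grade 1 by then causes no delay and costs 3 doses. Whether this exceeds the 3-day limit depends on counting omitted dosing days (3) or calendar days (7); 5.4 does not say. If the value is still above Grade 1 on Day 29, the any-delay sentence makes it a DLT at once. Condition (d), counted from Day 22, would wait until Day 22 + 14 = Day 36, and the 5.2 delay bullet would need more than 14 days beyond Day 29.

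**3. Effect of one reclassified patient under the 3+3 rules** (Protocol 5.1.1)

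| Count | With one more DLT | Level 1 (150 mg) | Level 2 (200 mg) |
|---|---|---|---|
| 0/3 | 1/3 | add 3 patients instead of escalating | no change if it becomes the RP2D, since 6 evaluable are needed |
| 1/3 | 2/3 | recruitment stops | fall back to level 1 |
| 0/6 | 1/6 | no change | no change |
| 1/6 = 16.7% | 2/6 = 33.3% | recruitment stops | fall back to level 1 |

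Removing a DLT has the reverse effect. At most 12 evaluable patients are planned. No probability is attached, because the documents give no rate of such values.

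**The case against.** The strongest reply is that the text gives one answer. The 5.2 list is disjunctive, its last bullet stands apart from the others, Table 5-3 forces an interruption, and the Grade 3 adjustment sentence is specific and mandatory whereas the 3-day sentence is general and permissive. On that reading the value is a DLT. This is a fair literal reading, but it confirms the defect: conditions (a) to (d) are left nearly inoperative.

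The opposite reply is that the 5.4 lead-in carries the conditions over, since it ties the list to DLT criteria. That is arguable but not secure. The list repeats the 5.2 qualifiers for thrombocytopenia, Hy's law and clinical Grade 3 toxicity, and the laboratory exclusions, yet omits only these conditions. It also goes beyond the DLT criteria, for example "more than six Debio 1143 skipped doses during any cycle due to treatment-related toxicity or more than 2 treatment interruptions" lasting more than 24 hours but under 6 days.

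One objection narrows the point. Table 7-2 directs immune-related Grade 3 hepatic and renal toxicity to permanent discontinuation, and required withdrawal is already a DLT under 5.2. Those values are outside this point.

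Divergence between sites is limited. Dose decisions are taken at DSMC meetings (Protocol 11.6.3), the committee includes all active investigators (10.2.1), and DLTs are confirmed there.

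A reader might infer that the only possible error is over-counting. That would require knowing that the conditions were meant to govern. If the literal rule was intended and the conditions were applied, the count is too low.

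**Conclusion.** Wrong as written; minor. For related, non-excluded Grade 3 non-haematologic laboratory values in Cycle 1, outside the immune-related hepatic and renal cases, the DLT rule nearly cancels its own conditions, and neither document says which text prevails. The Cycle 2 delay rule has a separate, plain contradiction. The count can err in either direction. A single patient can change a dose decision, but only at the counts shown above.

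A reader might go further and infer that the RP2D is wrong. The documents do not support this: they contain no DLT data. SAP 4.3 records futility of the Part B cohorts, so escalation is over. SAP 16.1 sets the planned Debio 1143 dose at 20 × 200 = 4000 mg per cycle, which suggests, without stating it, that the RP2D was the 200 mg maximum. If so, over-counting did not lower the dose. Whether any DLT was missed cannot be judged from the plan. What remains is how to read the Cycle 1 DLT counts by dose level that the SAP still plans to report.

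**What to change.** **Protocol wording, including any reuse of this text**

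- Because the conditions stand in both 5.2 and the synopsis, give them effect. Add to the last DLT bullet in both places that a reduction triggered only by a Grade 3 laboratory value counts as a DLT only if (a and b), or c, or d holds. Leave the 5.4 reductions unchanged for safety. The skipped-dose bullet would still apply.
- Change the Cycle 2 delay sentence after Table 5-3 to more than 2 weeks, as in 5.2.
- State in 5.4 whether the 3-day sentence or the Grade 3 adjustment sentence prevails.

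**Study report.** State which rule was applied in Part A, and identify any Cycle 1 Grade 3 laboratory value whose DLT status depends on it. Use the DLT listing (SAP 18), the TEAE listing with relatedness and action taken (SAP 18.1) and the listing of new Grade 3/4 laboratory toxicities (SAP 18.3). The dose-reduction summary (SAP 18.1.7) is not enough: it tabulates reductions made, not reductions required, and is not by patient.

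**Cost.** A few lines of wording and one statement in the report, covering at most 12 planned evaluable patients. No new analysis is needed; relatedness and action taken are already collected in the eCRF.
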